### Myocardial Infarction

Myocardial infarction (MI) classification and criteria for diagnosis is defined by MVARC, which incorporates elements of the Third Universal definition of MI [72], [85].

MI Type	Definition
Periprocedural MI (<math>\leq 48</math> hours after the index procedure)	
 
• New ischemic symptoms (e.g., chest pain or shortness of breath), or new ischemic signs (e.g., ventricular arrhythmias, new or worsening heart failure, new ST-segment changes, hemodynamic instability, new pathological Q-waves in at least two contiguous leads, imaging evidence of new loss of viable myocardium or new wall motion abnormality) AND
 
• The peak CK-MB measured within 48 h of the procedure rises to <math>\geq 10</math>x the local laboratory ULN plus new ST-segment elevation or depression of <math>\geq 1</math> mm in <math>\geq 2</math> contiguous leads (measured 80 ms after the J-point), or to <math>\geq 5</math>x ULN with new pathological Q waves in <math>\geq 2</math> contiguous leads or new persistent LBBB, OR in the absence of CK-MB measurements and a normal baseline cTn, a cTn (I or T) level measured within 48 h of the PCI rises to <math>\geq 70</math>x the local laboratory ULN plus new ST-segment elevation or depression of <math>\geq 1</math> mm in <math>\geq 2</math> contiguous leads (measured 80 ms after the J-point), or <math>\geq 35</math>x ULN with new pathological Q waves in <math>\geq 2</math> contiguous leads or new persistent LBBB.
 

Spontaneous MI (<math>>48</math> hours after the index procedure)	
 
• Detection of rise and/or fall of cardiac biomarkers (preferably troponin) with at least one value above the 99th percentile URL, together with the evidence of myocardial ischemia with at least one of the following: 
 
○ ECG changes indicative of new ischemia (new ST-T changes or new left bundle branch block (LBBB))
 
○ New pathological Q-waves in at least two contiguous leads
 
○ Imaging evidence of a new loss of viable myocardium or new wall motion abnormality
 
○ Sudden, unexpected cardiac death, involving cardiac arrest, often with symptoms suggestive of myocardial ischemia, and accompanied by presumable new ST elevation, or new LBBB, and/or evidence of fresh thrombus by coronary angiography and/or at autopsy, but death occurring before blood samples could be obtained, or at a time before the appearance of cardiac biomarkers in the blood.
 
 
 

MI Type	Definition
	
 
○ Pathological findings of an acute myocardial infarction.
 

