3.2 Adverse Events

All serious adverse device or procedure effects and UADEs will be summarized for all subjects who are randomized (ITT population of Randomized cohort) or underwent an attempted procedure (AP population for Non-repairable or Severe MAC Cohorts) in this trial in terms the number of events, the percentage of subjects with events. All CEC adjudicated adverse events will also be summarized similarly for all mITT, PP and AP populations. Moreover, COVID-19 related AEs will be summarized in terms of number of events, the percentage of subjects with events per MedDRA code.

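### As printed, the spontaneous MI definition places sudden death before blood sampling under a mandatory biomarker change, so that route can never qualify an event

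*Protocol*

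**What the plan says.** The Myocardial Infarction entry in Protocol Appendix II opens with its sources: "Myocardial infarction (MI) classification and criteria for diagnosis is defined by MVARC, which incorporates elements of the Third Universal definition of MI". For events more than 48 hours after the index procedure it prints a single top-level bullet: "Detection of rise and/or fall of cardiac biomarkers (preferably troponin) with at least one value above the 99th percentile URL", and then the connector "together with the evidence of myocardial ischemia with at least one of the following".

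Five sub-bullets follow: ECG change, new Q-waves, imaging evidence, sudden cardiac death, and pathology. The sudden-death item asks for presumed new ST elevation, new LBBB or fresh thrombus at angiography or autopsy, and ends with "death occurring before blood samples could be obtained, or at a time before the appearance of cardiac biomarkers in the blood". The fifth item reads "Pathological findings of an acute myocardial infarction". It has the same sub-bullet mark, but in the text available to us it falls on a continuation row after the table header is repeated.

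Nothing elsewhere in the protocol or SAP says that either of the last two items can stand alone.

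On use of the label, MI is an anticipated event in Protocol Table 4, and Protocol 12.11.5 gives the CEC the adjudication of adverse events. SAP 3.2 adds: "All CEC adjudicated adverse events will also be summarized similarly for all mITT, PP and AP populations".

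**The concern.** The sudden-death item exists to capture infarctions that kill before a biomarker can show them. Placed under a compulsory biomarker change, it contradicts its own lead-in. A committee applying the text literally would have to refuse the MI label to exactly the deaths that the item describes. If pathology is nested in the same way, an infarct seen at autopsy without a biomarker result would be refused as well.

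The situation can arise. Under Protocol 8.2, CK-MB or troponin at follow-up visits is drawn only when indicated, so a sudden death away from hospital may well have no sample.

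At stake is the MI line in the adverse event tables, which could omit some of the most severe infarctions. There is also an inconsistency within Appendix II. The cardiovascular death definition names MI as a proximate cardiac cause without any biomarker condition, so one event could be a cardiovascular death from MI under that entry and not an MI under this one.

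**Working it through.** No sample size, power or alpha is involved, and the plan gives no figure to reproduce. The check is one of logic.

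**Notation** (all from the MI entry in Appendix II)
- B: biomarker rise and/or fall with at least one value above the 99th percentile limit
- E: ECG, Q-wave or imaging evidence
- S: the sudden-death item, including its ECG, angiographic or autopsy evidence
- P: pathological findings of acute MI

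**Printed rule:** MI = B AND (E OR S OR P)

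**Rule with stand-alone alternatives:** MI = (B AND E) OR S OR P

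**Step 1.** S describes a death before sampling or before biomarkers appear, so S implies not-B. Hence B AND S is always false, and under the printed rule S can never be the item that qualifies an event.

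**Step 2.** Apply both rules to deaths after 48 hours.

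| Case | B | Other evidence | Printed rule | Alternatives rule |
|---|---|---|---|---|
| 1. Qualifying biomarker change plus ECG, Q-wave or imaging evidence | yes | E | MI | MI |
| 2. Qualifying biomarker change plus infarct at autopsy | yes | P | MI | MI |
| 3. Sudden death before sampling, with new ST elevation, LBBB or fresh thrombus | no | S | not MI | MI |
| 4. Infarct at autopsy, no biomarker result | no | P | not MI, if P is nested | MI |
| 5. Sudden death, no sample, no ECG, angiogram or autopsy | no | none | not MI | not MI |

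Only cases 3 and 4 change. Case 4 depends on the layout of the pathology item; case 3 does not.

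**Step 3.** Where the label is used.
- Primary endpoint, all cohorts: death from any cause and heart failure hospitalization. The death counts whatever it is called.
- Secondary endpoints: none has MI as a component.
- MVARC Procedural Success (descriptive, 30 days): MI is item 2g, within a list of device- or procedure-related serious events. A related death already fails item 2a, so the effect is marginal at most.
- Descriptive composite from 2 years: the cardiovascular hospitalization definition names acute MI as an example, but the composite already counts every death.
- Adverse event tables (SAP 3.2): the MI count can be too low.

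**Step 4.** Size. Let f be the share of MIs after 48 hours in which death precedes a qualifying biomarker result, and e the share of those deaths with the ECG, angiographic or autopsy evidence that the definition requires. The share of MIs missed is about f × e. The documents give neither quantity and no MI rate. Purely as an assumption, f of 10% to 30% gives 10% to 30% when e = 1 and 0% when e = 0. The result only repeats what was assumed.

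**The case against.** The strongest reply is that this is a formatting slip and that a competent committee would read through it. An item that speaks of death before blood could be drawn makes no sense if a sample is required, and the adjudicators are qualified physicians. They work to a separate CEC Charter, which is not among the documents and may already hold a working rule. The definition also points to published sources that are not available here. This stands as a limit: the documents do not show that any event has been or would be misclassified. It does not remove the contradiction, because the printed rule gives the wrong answer if followed, and the definitions in Appendix II are those the protocol says it will use.

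A second reply is that the pathology item is separated from its parent by a table break in text read from PDF, so its nesting is uncertain. That is correct, and the point about pathology is conditional for that reason.

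A third is that the affected deaths are not lost. Sudden death, and death from MI, both count as cardiovascular under Appendix II with no biomarker needed. That is also correct; only the MI label is at issue. Nor is it settled that every MI goes to the CEC. The opening of Appendix II promises adjudication of events that constitute primary or secondary endpoints, and Protocol 12.7.4 sends on those serious events that require it.

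A reader might infer that no fatal MI after 48 hours can be adjudicated as MI. The documents do not support this: cases 1 and 2 qualify under the printed text. Nor do they support saying that every unsampled fatal MI is lost through the nesting. Case 5 fails under either rule because the evidence that the definition requires is absent.

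**Conclusion.** The point holds in a narrow form. The sudden-death item contradicts its lead-in and cannot operate. As written, a sudden death after 48 hours with the listed ECG, angiographic or autopsy evidence but no qualifying biomarker result is not an MI. The same applies to an autopsy-proven infarct without a biomarker result, provided the pathology item is nested as its bullet mark suggests.

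The consequence is minor: a possible small undercount of MI among adjudicated adverse events, with no effect on any primary or secondary endpoint, on power or on alpha. The size cannot be estimated from the documents. The conclusion rests on two assumptions: that the printed layout is the intended rule, and that the CEC Charter does not already override it.

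**What to change.** In Appendix II, set out the definition for events after 48 hours as three alternatives, any one sufficient:

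1. the biomarker criterion together with ECG, Q-wave or imaging evidence;
2. the sudden-death item with its existing ECG, angiographic or autopsy evidence, and no biomarker requirement;
3. pathological findings of acute MI, and no biomarker requirement.

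Check the CEC Charter and align it if it differs. Ask the CEC which reading it has applied, and re-check sudden deaths already adjudicated only if it used the nested one.

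The cost is moving two bullets, possibly a charter update, and at most a re-review of the sudden deaths already adjudicated. Events that already qualify do not change. The downside is that reported MI counts may rise slightly.

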### New York Heart Association Classification (NYHA Class):

Class	Definition
I	Patients with cardiac disease but without resulting limitations of physical activity.
II	Patients with cardiac disease resulting in slight limitation of physical activity. Patients are comfortable at rest. Ordinary physical activity results in fatigue, palpitation, dyspnea, or anginal pain.
III	Patients with cardiac disease resulting in marked limitation of physical activity. Patients are comfortable at rest. Less than ordinary physical activity causes fatigue, palpitation dyspnea, or anginal pain.
IV	Patients with cardiac disease resulting in inability to carry on any physical activity without discomfort. Symptoms of cardiac insufficiency or of the anginal syndrome may be present even at rest. If any physical activity is undertaken, discomfort is increased.

### Principal Investigator (from ISO 14155)

Qualified person responsible for conducting the clinical investigation at an investigation site. If a clinical investigation is conducted by a team of individuals at an investigation site, the principal investigator is responsible for leading the team.

### Randomization (from ISO 14155)

Process of assigning subjects to the investigational medical device or comparator groups using an established, recognized statistical methodology to determine the assignment in order to reduce bias.

### Repositioning (from ISO 5840-3)

Change in implant position of a partially or fully deployed transcatheter heart valve substitute via a transcatheter technique, possibly requiring full or partial recapturing of the device.

### Retrieval (from ISO 5840-3)

Removal of a partially or fully deployed transcatheter heart valve substitute via a transcatheter technique.

### Single Leaflet Device Attachment (SLDA)

The loss of insertion of a single leaflet from the MitraClip device with ongoing insertion of the opposing leaflet [65].

### Stroke and TIA (from VARC II)

The following stroke and TIA diagnostic criteria will be used in this trial, per VARC II [80]:

- Acute episode of a focal or global neurological deficit with at least one of the following: change in the level of consciousness, hemiplegia, hemiparesis, numbness, or sensory loss

affecting one side of the body, dysphasia or aphasia, hemianopia, amaurosis fugax, or other neurological signs or symptoms consistent with stroke.

- **Stroke:** Duration of a focal or global neurological deficit  $\geq 24$  hours; OR  $< 24$  hours if available neuroimaging documents a new hemorrhage or infarct; OR the neurological deficit results in death.
- **TIA:** Duration of a focal or global neurological deficit  $< 24$  hours, any variable neuroimaging does not demonstrate a new hemorrhage or infarct.
- No other readily identifiable non-stroke cause for the clinical presentation (e.g., brain tumor, trauma, infection, hypoglycemia, peripheral lesion, pharmacological influences), to be determined by or in conjunction with the designated neurologist.
- Confirmation of the diagnosis by one of the following:
  - Neurologist or neurosurgical specialist
  - Neuroimaging procedure (CT scan or brain MRI), but stroke may be diagnosed on clinical grounds alone.

### Stroke Classification

The following stroke definitions will be used, per VARC II [77].

- **Ischemic:** An acute episode of focal cerebral, spinal, or retinal dysfunction caused by infarction of the central nervous system tissue.
- **Hemorrhagic:** An acute episode of focal or global cerebral or spinal dysfunction caused by intraparenchymal, intraventricular, or subarachnoid hemorrhage.

**Note:** A stroke may be classified as undetermined if there is insufficient information to allow categorization as ischemic or hemorrhagic.

### Structural Valve Dysfunction

Structural valve dysfunction will apply to Tendyne only, and will be defined as hemodynamic dysfunction (moderate or severe) in the presence of morphologic dysfunction. These definitions were adapted based on the EAPCI Consensus Statement [86] and the ASE Guidelines [87]:

[figure not shown]
Type of Valve Dysfunction	Definition
Moderate hemodynamic dysfunction	
 
• Mean transvalvular gradient 6-10 mmHg OR
 
• Moderate transvalvular regurgitation (grade 2-3+)
 

Severe hemodynamic dysfunction	
 
• Mean transvalvular gradient <math>> 10</math> mmHg OR
 
• Severe transvalvular regurgitation (grade 4+)
 

Morphologic dysfunction	
 
• Leaflet abnormalities resulting in stenosis and/or central regurgitation, including:           
 
○ Integrity – torn or flail
 
○ Structure – thickening or calcification
 
○ Function – impaired mobility
 
 
 

Type of Valve Dysfunction	Definition
	

• Strut/frame fracture

• Tether rupture

• Apical pad deterioration

**Society of Thoracic Surgeons (STS) Predicted Risk of Mortality (PROM) Score**

STS PROM scores for both “MV Replacement Only” and “MV Repair” will be calculated in the trial for the Tendyne device and Control group subjects. The risk calculators can be completed online at <http://riskcalc.sts.org/>.

**APPENDIX III: SUBJECT SCREENING FLOW CHART**

## APPENDIX IV: TRIAL ASSESSMENT AND FOLLOW-UP SCHEDULE

Exams, Tests and Data Collection	Screening / Baseline	Procedure	Pre-discharge	1 Month	3 Months*	6 Months	1 and 2 years	Annual visits (3-5 years)
Visit Window		Before and After Implant	72 hours prior to discharge	-3 days +14 days	±30 days	±30 days	±30 days	±45 days
Informed Consent	X							
Inclusion/Exclusion Screening	X							
Medical history with Demographics	X							
Physical Exam including Vital Signs while sitting	X		X	X		X	X	X
Cardiovascular Medications	X	X	X	X	X	X	X	X
Essential Frailty Toolset (EFT)	X							
STS PROM Risk Score	X							
CCS Angina Classification	X							
NYHA Classification	X			X		X	X	X
Modified Rankin Scale (mRS ‡ )	X							
Six Minute Hall Walk Test	X			X		X	X	X
KCCQ	X			X		X	X	X
EQ-5D	X			X		X	X	X
SF-12	X			X		X	X	X
CLINICAL LABORATORY TESTS								
Pregnancy Test	X							
Creatinine	X		X	X		X	X	X
Plasma-free Hemoglobin	X			X		X	X	X
BNP or NT pro-BNP	X			X		X	X	X
International Normalized Ratio (INR)	X		X	X		X	X	X
Creatine Kinase-MB (CK-MB) if indicated	X		X	X		X	X	X
Troponin (Type I or T) if indicated	X		X	X		X	X	X
Serum albumin	X							
INTRAOPERATIVE HEMODYNAMICS – (Tendyne Only)								
Cardiac Output		X						
PA Pressures		X						
RA Pressures		X						
Aortic pressures		X						
LV Pressures		X						
EXAMS AND TESTS								
Coronary Angiogram (if clinically indicated)	X							
Cardiac CT ^	X			X				
ECG (12-Lead)	X	X	X	X		X	X	X
TEE	X	X						
TTE ^	X		X	X		X	X	X
OTHER								
Device Deficiencies		X						
Adverse Events		X	X	X	X	X	X	X
Protocol Deviations	X	X	X	X	X	X	X	X
COVID-19 Assessment	X	X	X	X	X	X	X	X

\*The 3 month visit will be conducted via telephone.

‡Modified Rankin Scale is also to be completed after suspected onset of stroke^

^TTE imaging must be conducted between 60 and 120 days after anticoagulation stoppage for subjects implanted with the Tendyne valve. If the TTE identifies suspected valve dysfunction, contrast-enhanced cardiac CT imaging is also required. If renal insufficiency precludes a cardiac CT, a TEE must be performed instead.

**Note:** Baseline imaging for Cardiac CT, TEE and TTE must be acquired no earlier than 120 days prior to subject consent.

**APPENDIX V: ESSENTIAL FRAILTY TOOLSET**

**APPENDIX VI: CONTACT INFORMATION**

## **APPENDIX VII: ACCOMPANYING INFORMATION**

Investigational device labels, case report forms, and informed consent form template have all been provided under separate cover and are available on request from the Sponsor.

A copy of the monitoring plan can be obtained on request from the Sponsor clinical project manager.

## APPENDIX VIII: NON-SUITABILITY CRITERIA FOR TEER

A horizontal bar chart with 10 bars. The bars are black with white outlines. The lengths of the bars decrease from left to right. The first bar is the longest, followed by a short white bar, then a medium black bar, then a long black bar, then a short white bar, then a medium black bar, then a long black bar, then a short white bar, then a medium black bar, and finally a very long black bar.

## APPENDIX IX: CLINICAL INVESTIGATION PLAN REVISIONS

The figure consists of a 3x3 grid of horizontal bar charts. Each bar is composed of two segments: a black segment on the left and a white segment on the right, separated by a thin white line. The length of the black segment varies across the bars. The bars are arranged in three rows: the top row has 10 bars, the middle row has 10 bars, and the bottom row has 10 bars. The bars are separated by thin white lines.

This figure consists of a 3x10 grid of horizontal bar charts. The first column contains a single black bar. The second column contains 10 bars, each with a white gap at the start. The third column contains 10 bars, each with a white gap at the end. The bars are black with white outlines.

The figure consists of a 3x3 grid of bar charts. The first two columns each contain a single bar per row. The third column contains 18 bars per row, with the first bar in each row being significantly shorter than the others. The bars are black with thin white outlines.

Page 111 of 122

The figure consists of three vertically stacked bar charts, each with 10 bars. The bars are black with thin white outlines. The first bar in each chart is the shortest, and the last bar is the longest. The charts are separated by white space.

## APPENDIX X MITRACLIP INDICATION FOR USE

- The MitraClip™ NTR/XTR Clip Delivery System is indicated for the percutaneous reduction of significant symptomatic mitral regurgitation (MR  $\geq 3+$ ) due to primary abnormality of the mitral apparatus [degenerative MR] in patients who have been determined to be at prohibitive risk for mitral valve surgery by a heart team, which includes a cardiac surgeon experienced in mitral valve surgery and a cardiologist experienced in mitral valve disease, and in whom existing comorbidities would not preclude the expected benefit from reduction of the mitral regurgitation.
- The MitraClip™ NTR/XTR Clip Delivery System, when used with maximally tolerated guideline-directed medical therapy (GDMT), is indicated for the treatment of symptomatic, moderate-to-severe or severe secondary (or functional) mitral regurgitation (MR; MR  $\geq$  Grade III per American Society of Echocardiography criteria) in patients with a left ventricular ejection fraction (LVEF)  $\geq 20\%$  and  $\leq 50\%$ , and a left ventricular end systolic diameter (LVESD)  $\leq 70$  mm whose symptoms and MR severity persist despite maximally tolerated GDMT as determined by a multidisciplinary heart team experienced in the evaluation and treatment of heart failure and mitral valve disease.

1.0 SYNOPSIS OF STUDY DESIGN

1.1 Purpose of the Statistical Analysis Plan

This statistical analysis plan (SAP) is to provide a detailed and comprehensive description of the planned methodology and analysis to be used for Protocol CS0004-P, [REDACTED], the SUMMIT clinical trial.

1.2 Clinical Investigational Objectives

The objective of the trial is to evaluate the safety and effectiveness of the Tendyne™ Transcatheter Mitral Valve System for the treatment of patients with symptomatic, moderate-to-severe or severe mitral regurgitation (MR), or for patients with symptomatic mitral valve disease due to severe mitral annular calcification..

1.3 Clinical Investigational Design

This trial is a prospective, controlled, multicenter clinical investigation of the Tendyne™ Transcatheter Mitral Valve System for the treatment of eligible subjects with symptomatic, moderate-to-severe or severe mitral regurgitation (MR; MR \geq Grade III per American Society of Echocardiography criteria), or severe mitral annular calcification (MAC) for whom the site heart team deems transcatheter treatment is more appropriate than conventional mitral valve surgery.

The trial is composed of a Randomized, a Non-repairable and a Severe MAC Cohort. Subjects will be assigned to either the Randomized, the Non-repairable or the Severe MAC Cohort at the discretion of the local site heart team. Subjects must satisfy the trial inclusion/exclusion criteria and be approved by the Subject Eligibility Committee (SEC), prior to inclusion in the trial.

Randomized Cohort: Subjects suitable for transcatheter mitral valve replacement (TMVR) with Tendyne and indicated for transcatheter edge-to-edge repair (TEER) with MitraClip will be randomized in a 1:1 ratio to receive either Tendyne (Treatment) or MitraClip® (Control). Subjects with primary MR must be at prohibitive surgical risk, while subjects with secondary MR must be symptomatic despite maximally-tolerated guideline-directed medical therapy in accordance with the MitraClip Indications for Use. Randomization will be stratified by investigational site.

Non-Repairable Cohort: Subjects with valve anatomies suitable for Tendyne TMVR, but not for TEER will be eligible to enroll in the Non-repairable Cohort, in which all subjects will receive treatment with the Tendyne system.

Severe MAC Cohort: Subjects who have severe MAC rendering the subject unsuitable for mitral valve surgery will be eligible to enroll in the Severe MAC Cohort, in which all subjects will receive treatment with the Tendyne system.

Approximately 382 subjects will be included in the Randomized Cohort, with approximately 191 subjects targeted to receive the investigational device, at up to 80 sites in globally. In the Non-repairable Cohort, approximately 325 subjects will be targeted to receive the investigational device. In the Severe MAC Cohort, approximately 103 subjects will be targeted to receive the investigational device. [REDACTED]

[REDACTED]

Statistical Analysis Plan

Following the completion of enrollment of the Severe MAC Cohort, approved subjects will be enrolled into a Severe MAC continued access plan (CAP). Details of the analysis plan for the Severe MAC CAP are included in APPENDIX VI.

An additional 160 roll-in subjects (up to 2 per site) may be treated by operators without prior or recent experience using the Tendyne system to gain hands-on experience before registering subjects in a study cohort. Roll-in subjects will not count toward the subject caps in the Randomized (382 subjects), Non-repairable (325 subjects) cohort or Severe MAC (103 subjects) cohorts.

All subjects will be followed at 30 days, 90 days, 6 months, 12 months, and annually thereafter through 5 years from the index procedure.

